to significantly increase both linkage to and retention in care. While ARTAS was developed for new-to-care PLWH, BA2C was tailored and adapted for PLWH who had previously linked to but were not currently engaged in care. BA2C results showed that participants in both the intervention and comparison groups improved across multiple outcomes (linkage to care, retention in care, ART prescription, and viral suppression), but there was no significant difference between groups. Some of the limitations of the BA2C study included poor retention rates (70%) and difficulty attending CHW intervention sessions, suggesting that a hybrid intervention in which CHW sessions can be delivered through a mobile platform has the potential to improve the efficacy of the intervention. Given the limitations of the BA2C intervention^{59, 60} and in direct response to RFA-NR-20-002, *Strengthening the Impact of Community Health Workers on the HIV Care Continuum in the US*, we will leverage our mHealth work to overcome the limitations of the BA2C study. Namely, we will use mHealth technology to overcome logistic hurdles of connecting participants and their CHW and to improve engagement through the tools in our WiseApp.

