(WiseApp). Guided by a rigorous theoretical model of supportive accountability, the literature and our preliminary work support the scientific premise that adding WiseApp to the CHW intervention will enable PLWH to self-manage their ART regimens while CHW monitor their ART adherence in real-time ultimately leading to viral suppression and ART adherence. The proposed study will provide further information regarding the successful wide-scale implementation of this combination intervention in two high priority settings.

The proposed study will test the clinical efficacy and assess the implementation factors of the resultant CHW intervention, **Community Health Worker And MHealth to ImProve Viral Suppression (CHAMPS)**, through the following specific aims with virally unsuppressed adult PLWH (n=150 in AL and 150 in NYC):

1: Conduct an RCT to assess the efficacy and sustainability of CHAMPS on viral suppression (primary outcome) and ART adherence (secondary outcome) compared to the standard of care (standard of care, control group) over 6 and 12 months.

PLWH randomized to CHAMPS will have significantly greater:

H₁: Viral suppression (primary outcome) than those in the standard of care group.

H₂: ART adherence (secondary outcome) than those in the standard of care group.

2: Identify mediators and moderators of CHAMPS on study outcomes.

H₃: HIV medication taking self-efficacy, motivation expectancies, self-regulation skills, and HIV-related stigma mediate the effect of CHAMPS on viral suppression and ART adherence.

H₄: Depression, anxiety, and substance use moderate the strength of the effect of CHAMPS on viral suppression and ART adherence.

3: Guided by the Reach Effectiveness Adoption Implementation Maintenance (RE-AIM) framework, identify multi-level factors associated with successful implementation of CHAMPS to inform future implementation and scale-up.

This study seeks to expand and strengthen a CHW model through an extant mHealth approach. Findings will inform the effect of CHAMPS on outcomes related to the HIV Care Continuum in two EHE priority settings.

Theoretical Framework

The intervention is guided by the conceptual model of supportive accountability illustrated in **Figure 1**.⁸⁶ The model is based on the premise that human support increases medication adherence through accountability to a coach (in CHAMPS – a CHW) who is perceived as trustworthy, knowledgeable, and benevolent.

[figure not shown]

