Limitations and Considerations of the Study Outcome. We recognize that all the approaches for measuring viral suppression and ART adherence are limited. First, viral suppression does not directly measure a behavioral outcome but, rather, the biologic effects of the behavior. Second, the self-report measure is biased and has ceiling effects. Finally, the electronic pill box is limited to data collected from the intervention group. While this is a limitation, providing the electronic pillbox to the standard of care (control group) is likely to bias our intervention effects since this pillbox will, in fact, have intervention effects as we have found from our preliminary findings from our WiseApp trial. We closely considered each of these limitations and have, therefore, decided that this three-pronged (i.e., viral load, self-report, and electronic pillbox) approach which will provide the most rigorous approach to measuring our primary and secondary outcomes of viral suppression and ART adherence.

Mediators

Several mediators are hypothesized to explain the mechanisms through which the intervention is anticipated to improve viral suppression. Hypothesized mediators include: self-efficacy, motivation expectancies, self-regulation skills, and HIV-related stigma. The HIV Medication Taking Self-Efficacy Scale is also used to measure ART adherence self-efficacy, or the confidence to take medications in various situations.¹²⁸ Motivation and outcome expectancies of ART adherence are assessed as three separate dimensions: attitudes, norms, and behavioral intentions to adhere to ART medication.¹¹⁸ Self-regulation skills, which include self-monitoring, goal-setting, and enlistment of self-incentives/plans, are also assessed.¹¹⁹ In prior studies of ART adherence, HIV-related stigma and discrimination have been strongly associated with non-adherence;^{14, 129} thus, we also measure HIV-related stigma.

Moderators

Several moderators are hypothesized to affect the strength of the intervention to yield improvements in viral suppression and will be explored. Hypothesized moderators include: depression, anxiety and substance use.

Table 4. Measures and Schedule of Events

	Screening	Baseline	6 mos	12 mos
Sociodemographic: (e.g., age, race/ethnicity, education, housing)		X		
Primary Outcome Measures				
Viral Load through a blood draw	X		X	X
Secondary Outcome Measures				
ART adherence (SRSI) ¹⁰¹ and the CleverCap (intervention group only)	X		X	X

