The primary hypothesis 1 (H_1) will be tested using a generalized linear mixed model (GLMM) with logit-link function for binary outcomes (i.e., viral suppression) or a linear mixed model (LMM) for continuous outcomes (i.e., viral load measured in logarithmic scale) to account for the non-independence of repeated measurements within individuals.¹³³ The models will include a random intercept and fixed effects for intervention group, time, and interaction term of group and time which is for testing efficacy of the intervention. The model may include stratification variables, such as study site, age, and sex as covariates. A site by group interaction will be also examined and included in each model (above) if significant at the .05 level. All analyses will be tested for goodness-of-fit using the Wald-type test, which shows satisfactory performance for models with fewer (<5) covariates.¹³⁴ A similar GLMM will be used to test sustainability of the intervention at month 12. For this analysis, we will conduct a non-inferiority test¹³⁵ to compare viral suppression rate between month 12 and month 6. For primary hypothesis 2 (H_2), testing for intervention effect on ART adherence measured by SRSI (secondary outcome), we will use a similar LMM as mentioned above. For electronic pill bottle data in the intervention group, we will also examine the trend of electronic pill bottom data over time with a GLMM which will include a first-order autoregressive (AR1) covariance structure, as described by Hedeker and Gibbons.¹³³ We will also aggregate the electronic pill bottle data at different time points (0, 6, and 12 months) and examine the association between the electronic pill bottle data and ART adherence data measured by SRSI using Spearman nonparametric correlation.¹⁰¹ Similar GLMMs or LMMs will be used for secondary outcomes, with GLMMs for binary outcomes and LMMs for continuous outcomes.

Aim 2: Identify mediators and moderators of CHAMPS on study outcomes.

Data Analysis

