Mediators. If the intervention arm shows improved viral suppression in greater magnitude than the standard of care, we will explore the extent to which this relationship works through several possible mediators, including: self-efficacy, motivation expectancies, self-regulation skills, and HIV-related stigma. For mediation analyses, we will employ MEDIATE procedures.¹³⁰ MEDIATE estimates the total, direct, and indirect effects of causal variable(s) (xlist) on the outcome variable (yvar) through a proposed mediator variable or set of mediator variables (mlist), controlling for (optional) one or more variables in (covlist). MEDIATE is similar to INDIRECT¹³⁶ but allows multiple variables and also offers features for handling and coding a single multi-categorical variable. Inferences for indirect effects can be based on either percentile bootstrap confidence intervals or Monte Carlo confidence intervals. For effect modification analyses, we will add interaction terms one-by-one for the intervention condition and the potential moderators (e.g., depression). Significant or large interaction terms suggest that the effects of the intervention differ for different subgroups, as defined by the moderators.

Moderators. In addition, we will study the moderators of treatment effect. This is a potentially impactful goal, given the gradual but assured paradigm shift in behavioral interventions from a “one-size-fits-all” approach to modern personalized medicine. Potential moderators in the current context are depression, anxiety and substance use. Regression analysis including potential moderators in the model as interaction terms will be conducted. If any interactions are significant, then patient characteristics can be used to better inform dissemination of this intervention. Moderation analysis will be performed using the R software package qLearn.¹³⁷

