Efficacy: The impact of an intervention on outcomes including potential negative effects, quality of life.	
Did the intervention achieve primary and secondary outcomes?	Between-group comparisons on primary and secondary outcomes (Aim 1)
Did it produce unintended adverse consequences?	Review notes from participant study withdrawal, Notifications to the IRB about participant complaints
What effect did the mediators and moderators have on the primary and secondary outcomes?	Data analyzed in Aim 2
Adoption: The absolute number, proportion, and acceptability of CHAMPS; proportion of eligible patients that enroll.	
Did the intervention help the organization address its mission, values, and priorities?	Key informant interviews with clinic staff, research staff, CHW, and administration - descriptive, interpretative analysis for key themes
Implementation: At the setting level, includes consistency of delivery and predisposing, enabling, and reinforcing factors. At the individual level, implementation refers to individual's use of strategies. ¹⁵²	
Were intervention components delivered as intended?	Paradata Analysis –App use by component
What barriers to implementation were identified and how were they addressed?	Key informant interviews with study staff; In-depth interviews with study participants. - descriptive, interpretative analysis for key themes
What enabling (facilitating) factors were required to support the intervention?	Project meeting minutes Interviews with stakeholders
Maintenance: Individual – Understanding Use of the App over time.	
Did the intervention produce lasting effects at individual level?	Long-term efficacy of CHAMPS intervention over 12 months
Is there the potential for sustaining CHAMPS over time?	Key informant interviews with clinic staff, research staff, CHW and clinicians, CBO staff and study participants.
How did the intervention evolve?	Project meeting minutes; Paradata

implementation evaluation for this proposal; [name] will provide oversight, along with MPIs [name] and [name], for all implementation activities.

Process Evaluation Outcomes

The RE-AIM evaluation dimensions and associated measures in our study are summarized in Table 5. In addition to testing the **Efficacy** of CHAMPS, we will concurrently measure the four remaining RE-AIM dimensions¹⁵¹ as follows:

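### Mediation is conditional on an undefined improvement in viral suppression and is specified only for that outcome, although H3 also covers ART adherence

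*Combined protocol and SAP*

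**What the plan says.** H3, in the specific aims under Study Purpose and Rationale, names two outcomes: "HIV medication taking self-efficacy, motivation expectancies, self-regulation skills, and HIV-related stigma mediate the effect of CHAMPS on viral suppression and ART adherence".

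The Mediators paragraph of the Aim 2 Data Analysis section begins "If the intervention arm shows improved viral suppression in greater magnitude than the standard of care, we will explore the extent" and continues "to which this relationship works through several possible mediators, including: self-efficacy, motivation expectancies, self-regulation skills, and HIV-related stigma". The only relationship that the sentence has introduced is the one between arm and viral suppression. The MEDIATE procedure is then described generically, as estimating effects "on the outcome variable (yvar) through a proposed mediator variable or set of mediator variables (mlist"). Neither study outcome is assigned to that variable.

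Three other places bear on the point:

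- The Mediators subsection under Study Outcomes names viral suppression only: "Several mediators are hypothesized to explain the mechanisms through which the intervention is anticipated to improve viral suppression".
- The Efficacy part of Table 5 asks "What effect did the mediators and moderators have on the primary and secondary outcomes" and gives as its source the data analysed in Aim 2.
- The Aim 1 Data Analysis section covers adherence for H2: "testing for intervention effect on ART adherence measured by SRSI (secondary outcome), we will use a similar LMM as mentioned above". That is a test of the total effect, not a mediation model.

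**The concern.** The hypothesis and the analysis do not match in two ways.

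First, H3 has two outcomes and the analysis names one. Adherence is arguably the nearer outcome for these mediators. The Study Outcomes section says that adherence behaviour must change before viral load can, and most of the mediators are measured as attitudes, skills or confidence about taking medication.

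Second, permission to examine mechanism depends on a result for viral suppression alone. An observed total effect is not needed for an indirect effect to exist, and the named procedure estimates total, direct and indirect effects together without a prior screen. The plan also does not say whether the condition means a favourable point estimate or a significant test, which leaves the choice to be made after the data are seen.

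At stake is whether the trial can answer H3 when the outcomes diverge. The sponsor's earlier studies make that conceivable. The WiseApp trial's preliminary data showed an adherence benefit (58% against 47%, p=0.03). In BA2C both arms improved on outcomes that included viral suppression, "but there was no significant difference between groups".

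**Working it through.** **Text comparison**

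| Place | Outcome(s) for mediation | Condition |
|---|---|---|
| H3, specific aims | Viral suppression and ART adherence | None |
| Aim 2 heading | Study outcomes (plural, not named) | None |
| Mediators, under Study Outcomes | Viral suppression | None |
| Mediators, Aim 2 Data Analysis | Viral suppression; generic outcome variable in the MEDIATE description | Suppression must improve more under CHAMPS |
| Table 5, Efficacy | Primary and secondary | Refers back to Aim 2 |

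The only place that describes a mediation method is the fourth row. Table 5 sends the reader back to it, so the table does not supply an adherence model. Nowhere is there an unconditional mediation analysis, or one triggered by a result on adherence.

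**How often the condition would block mediation**

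Inputs from Sample Size and Power Calculation: 150 per arm, 80% retention (150 × 0.80 = 120 per arm), 75% reference suppression, a 12-point difference (87%), within-person correlation 0.6, two-sided α = 0.05. I assume that the control rate at six months is 75%.

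*The plan's own figures.* The arcsine effect size is 2·arcsin(√0.87) − 2·arcsin(√0.75) = 0.309, which matches the stated 0.31. Two-proportion power with the pooled null variance (mean rate 0.81) is:

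- 120 per arm: Φ[(0.12·√120 − 1.96·√(2·0.81·0.19)) / √(0.75·0.25 + 0.87·0.13)] = Φ(0.414) = 66%
- 150 per arm, same formula: 76%

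Multiplying the variance by (1 − 0.6²) = 0.64 for baseline adjustment, at 120 per arm:

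- SE = √(0.3006 × 0.64 / 120) = 0.0400
- power = Φ(0.12/0.0400 − 1.96) = 85%

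That is consistent with the stated minimum of 80%. The plan does not give its formula or say how the intra-cluster correlation of 0.2 enters, so no single value can be matched.

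*Reading A: direction only.* P(unmet) = 1 − Φ(d/SE), with SE = √[(0.75·0.25 + p₂(1−p₂))/120], p₂ = 0.75 + d, and no gain from the correlation:

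| True difference d | SE | d/SE | Unmet |
|---|---|---|---|
| 12 points | 0.0501 | 2.40 | about 1% |
| 10 points | 0.0512 | 1.95 | about 3% |
| 8 points | 0.0523 | 1.53 | about 6% |
| 0 | – | 0 | 50% |

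*Reading B: significant benefit.* P(unmet) = 1 − power:

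- At 12 points: 1 − 0.85 = 15% with the correlation gain and 1 − 0.66 = 34% without it. At the plan's stated power it is at most 1 − 0.80 = 20%.
- At no effect: 97.5%.

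These are normal approximations, not simulations of the planned mixed model.

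**Adherence.** Under either reading, the chance that a specified adherence mediation model is run is not a matter of power. No such model is written.

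**The case against.** The strongest reply is that this is an under-written sentence and not a decision to leave adherence out. The Aim 2 heading speaks of study outcomes, Table 5 refers to primary and secondary outcomes, and the described procedure can take any outcome. That stands as evidence of intent. A reader might infer that the trial will never examine mediation of adherence. The documents do not support that; they support only that no such analysis is specified.

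A reader might also infer that the condition means a significant H1 result, so that H3 would often go untested. The text does not say so. Elsewhere the authors state significance explicitly when they mean it, as for the site-by-group interaction and the moderator interactions. Direction only is the more natural reading, and under it the condition rarely blocks anything near the design effect.

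Three further points have some force:

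- The mediation work is worded as exploratory, and looking for an observed effect before exploring its mechanism is a common, if debated, convention. H3 itself speaks of mediating an effect. That would justify conditioning each outcome on its own effect. It does not justify conditioning adherence on suppression.
- The Aim 1 analysis will describe correlations of all variables with the primary and secondary outcomes unconditionally. This gives mediator-outcome associations, but not arm-to-mediator or indirect effects.
- The protocol attributes the BA2C null result to small sample size and 70% retention. BA2C therefore does not show that a null suppression result is likely here.

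**Conclusion.** The point holds as a mismatch between H3 and its analysis. Mediation is tied to an undefined improvement in viral suppression and is specified for that outcome only. If adherence improves and suppression does not, the plan as written triggers no mediation analysis.

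How often the condition blocks mediation depends on its meaning. If it is direction only, the figure is about 1% of trials at a true 12 points and about 50% at no effect. If it is significance, the figure is roughly 15-34% at 12 points, or at most 20% at the stated power. These figures assume 120 analysed per arm and a 75% control rate; the 15-34% range reflects whether the 0.6 correlation reduces the variance.

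It is tempting to add that selecting on a favourable result distorts the share attributed to the mediators. Under a significance condition the direction of that bias is plausible, but its size has not been worked out. Under the direction-only reading at the design effect, selection is negligible. I do not rely on it.

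The gap affects the exploratory Aim 2 analysis. It does not touch H1 or H2. It should be corrected, but it does not threaten the primary conclusion.

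**What to change.** In the Mediators paragraph of the Aim 2 Data Analysis section, delete the condition on viral suppression. State that exploratory mediation models will be fitted for viral suppression and, separately, for SRSI adherence, whatever the H1 result. SRSI is the adherence measure to use because the pill-bottle data exist only in the intervention arm. For each outcome, report the arm-to-mediator effect, the mediator-to-outcome effect and the indirect effect, with confidence intervals. Align the Mediators subsection under Study Outcomes so that it names both outcomes. Month-12 models are optional, since H3 does not call for them by time point.

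The cost is a few more exploratory analyses, to be labelled as such. Table 4 already schedules viral load, SRSI and all four mediators at 6 and 12 months, so no new data are needed.
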